## 9.6 Restrictions during the study

The subjects must be willing to comply to the following restrictions during the entire study duration *i.e.*, from screening to the end-of-study visit.

### 9.6.1 *General restrictions*

- Contraception Requirements:

The male subjects are expected to use condom to prevent pregnancy and drug exposure of a partner and refrain from donating sperm from the date of first dosing until three months after last dosing of the IMP. Female partners of child-bearing potential are expected to use contraceptive methods with a failure rate of < 1% to prevent pregnancy (for details, refer to inclusion criterion No 5) during the same period.

Female subjects of child-bearing potential must use effective contraception (defined in inclusion criterion No 5) or practice abstinence during the study and for 30 days after IMP administration. Female subjects must refrain from donating eggs from the date of dosing until 3 months after dosing with the IMP. Their male partner must agree to use a condom during the same time frame if he has not undergone vasectomy.

- Meals and Dietary Restrictions:

**Part I:** Subjects should be fasting overnight (10 hours) before IMP administration and until 4 hours post dose. IMP will be swallowed together with 240 mL tap water.

**Part II:** IMP will be administered within 30 minutes after intake of a standardised breakfast and swallowed together with 240 mL tap water.

For details on IMP administration in the fasted and fed state, refer to Section 10.5.

**Part I and Part II:** Standardised meals will be served while the study subjects are in the research clinic. Lunch will be served 4 hours post dose. Snack, dinner and evening snack will be served approximately 7, 9 and 11 hours post dose, respectively. Water is allowed ad libitum at the clinic except one hour before dose and one hour after dose on dosing days.

Standardised meals: A menu option (decided by CTC) will be offered while the study subjects are in the research clinic. The meal selection is standardised in the sense that the nutritional content of the meals should be similar at each time point of each treatment day.

- Alcohol: Consumption of alcohol is not allowed within 48 hours prior to the screening visit and prior to and during all subsequent clinic visits, including the end-of-study visit.
- Drugs of abuse: Use of drugs of abuse is not allowed during the study from screening to the end-of-study visit. In addition to the urine drug testing described in Table 8.1-1, additional random testing can be performed at the clinic visits.

- Caffeine: Consumption of up to 5 cups of coffee (or equivalent) per day will be allowed from 48 h before each visit and during each visit.
- Xanthine or taurine containing products/beverages: Energy drinks (e.g. Red bull) are not allowed during the study from 48 h prior to first IMP administration until the end-of-study visit.
- Nicotine: Smoking or use of nicotine-containing products is not allowed during the study from screening until the end-of-study visit.
- Grapefruit and grapefruit containing products: Consumption of grapefruit and/or grapefruit-containing products, Seville oranges is not allowed during the study from screening until the end-of-study visit.
- Blood donation: The subjects must not donate blood or plasma during the study from first IMP administration until three months after the end-of-study visit.
- Participation in other clinical studies: Study subjects are not allowed to participate in any other interventional clinical study during the study period.
- Sun protection: Protection from the sun is required from day of IMP administration (Day 1) until 48 h post dose (Day 3) in each sequence. Study subjects are required to follow the recommendations given by Centres for Disease Control and Prevention (CDC, see [15]):
  - Stay in the shade, especially during peak hours of 10 AM to 4 PM.
  - Wear clothing that covers arms and legs
  - Use a hat or cap that shades the face, head, ears and neck
  - Wear sunglasses that block both ultraviolet A (UVA) and ultraviolet B (UVB) rays
  - Proper use of a broad-spectrum sunscreen with a sun protection factor (SPF) of 15 or higher.
  - Abstain from use of tanning beds.
- Exercise: Subjects will abstain from strenuous exercise for 72 h before each blood collection for clinical laboratory tests.

### 9.6.2 *Prior and concomitant therapy*

#### Prohibited medication

Regular use of corticosteroids (inhaled and systemic), NSAIDs, aspirin, coxibs, antacids, PPIs or any other medication that changes gastric pH is prohibited from 14 days prior to first IMP administration until the end-of-study visit.

Use of corticosteroids (inhaled and systemic), NSAIDs, aspirin, coxibs, antacids, PPIs or any other medication that changes gastric pH, any other prescribed or non-prescribed medication, herbal remedies, vitamin supplements and minerals is prohibited from the first IMP administration until the end-of study visit, except as detailed below.

#### Allowed medication

- Paracetamol in doses up to 2000 mg/day for a maximum of 3 consecutive days. If this amount of paracetamol is not sufficient for treatment of the subjects, withdrawal should be considered.

- Nasal decongestants without cortisone, antihistamine or anticholinergics for a maximum of 10 days.
- Contraceptives.

Other medications considered necessary for the subject's safety and wellbeing may be given at the discretion of the Investigator during the residential period. Following consultation with the Sponsor, the Investigator will determine whether or not the subject should continue in the study.

## **9.7 Screen failures**

Screen failures are defined as subjects who consent to participate in the clinical study but are not subsequently dosed in the study. A minimal set of screen failure information is required to ensure transparent reporting of screen failure subjects. Minimal information includes documentation of signed and dated informed consent form (ICF) and reason(s) for screening failure.

Subjects who do not meet the criteria for participation in this study may be rescreened.

Re-screening can be performed once if any of the following were reasons for screening failure or not-dosing (as judged by the Investigator):

- Practical reasons.
- Non-significant medical conditions (e.g. influenza, nasopharyngitis).
- Plasma or blood donation outside allowed time windows.

For subjects who are re-screened, a new screening number will be assigned and a new, signed ICF will be collected.

## **9.8 Subject withdrawal**

### **9.8.1 *General withdrawal criteria***

Subjects are free to discontinue their participation in the study at any time and for whatever reason without affecting their right to an appropriate follow-up investigation or their future care. If possible, the reason for withdrawal of consent should be documented.

Subjects may be discontinued from the study at any time at the discretion of the Investigator.

Reasons for discontinuation include:

- Withdrawal of consent
- Severe non-compliance to study protocol procedures, as judged by the Investigator and/or Sponsor
- Subject is lost to follow-up.
- Significant AEs posing a risk for the subject, as judged by the Investigator and/or Sponsor
- Withdrawal of informed consent to the use of biological samples

- Pregnancy
- Death
- Meeting of an exclusion criterion during the study, which, in the opinion of the Investigator, may pose a risk for the subject

#### 9.8.2 *QTc withdrawal criteria*

A subject meeting the criteria below will be withdrawn from the study. The same QT correction formula will be used to determine discontinuation throughout the study.

- QTcF > 500 msec
- Change from baseline: QTc > 60 ms

Withdrawal decisions will be based on an average QTc value of triplicate ECGs. If an ECG demonstrated a prolonged QT interval, two more ECGs will be obtained over a brief period and the averaged QTc value of the three ECGs used to determine whether the subject should be discontinued from the study.

#### 9.8.3 *Liver chemistry withdrawal criteria*

Liver chemistry threshold stopping criteria have been designed to assure subject safety and to evaluate liver event aetiology. Study treatment will be stopped if any of the following liver chemistry stopping criteria, defined in the U.S. Food and Drug Administration (FDA) Guidance on Drug-Induced Liver Injury [16], is met:

- Alanine aminotransferase (ALT) 3 x Upper Limit of Normal (ULN) and total bilirubin  $\geq 2xULN$  (>35% direct bilirubin); **or** ALT 3xULN and INR > 1.5)

*NOTE: plasma bilirubin fractionation will be performed. Bilirubin is also measured via urine dipstick (a measurement of direct bilirubin, which would suggest liver injury).*

- ALT 5xULN.
- ALT 3xULN if associated with symptoms (new or worsening) believed to be related to hepatitis (such as fatigue, nausea, vomiting, right upper quadrant pain or tenderness or jaundice) or believed to be related to hypersensitivity (such as fever, rash or eosinophilia).
- Subjects with ALT 3xULN **and** < 5xULN **and** bilirubin < 2xULN, who do not exhibit hepatitis symptoms or rash, will be allowed to continue study treatment as long as they are monitored weekly for four weeks.

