#### **Safety assessments**

AE reporting, resting 12-lead ECG monitoring, vital signs (blood pressure and pulse), body temperature, physical examination, use of concomitant medications, urinalysis and blood sampling for haematology, clinical chemistry and coagulation parameters.

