### 6.3 Risk/benefit assessment

The healthy volunteers in this study will, except for thorough health examinations, have no medical benefit from participation and their safety and wellbeing are of utmost importance. The FIH study with GS-248, in which the SAD part with doses of 1-300 mg is finalised and did not reveal any noteworthy safety or tolerability findings at any dose level. The current study concerns a single dose of 120 mg in two different formulations, which is well beneath the maximum dose level studied in the FIH study. Adverse drug reactions (ADRs) are therefore not expected.

In a pre-clinical study, pronounced and serious effects on the liver and biliary system were noted in dogs at the highest dose in the 28-day toxicity study. However, no findings that were considered to constitute an adverse effect were noted at the intermediate dose level, primarily based on the total lack of treatment-related histopathological findings at this dose level, and the NOAEL in this study was therefore set at 20 mg/kg. The liver biomarkers will be closely monitored during the present study.

Subjects will remain in the research clinic for approximately 24 h after the single dose and will be closely monitored by medical staff. In addition, subjects will return to the clinic at approximately 48 h post dose for safety check-up.

Overdosing is not likely to occur since all IMP will be administered by site personnel under medical surveillance. In cases of accidental overdose, standard supportive measures should be adopted as required. For further information regarding overdosing, refer to Section 11.4.1.17.

The Principal Investigator at the research clinic will ascertain that adequate facilities and procedures are available to handle emergency situations should they occur during the study. The medical staff at CTC have extensive experience from early Phase I and FIH studies and there are adequate procedures in place to handle unexpected and expected adverse reactions in the study subjects. CTC has been regularly inspected by the Swedish Medical Products Agency (MPA) and is authorised to conduct early phase studies.

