### 8.1.2 ***Part II: Food interaction***

After evaluation of the PK profiles of Formulation A and B in Part I of the study, one formulation will be selected to be given following intake of a standardised breakfast in Part II of the study. In this part, any potential food interaction with GS-248 will be investigated.

After evaluation of the PK results from Part I, subjects will return to the clinic for a second dose of the selected formulation (Visit 6, similar to Visit 2), yet this time in fed conditions. The assessments during fed conditions will be the same as during fasting conditions (see Section 8.1.1), except for the fact that the subjects will consume a high-fat high-calorie breakfast 30 minutes prior to IMP administration as detailed in Section 10.5.

At 48 h post dose, subjects will return to the clinic for PK blood sampling and final end-of-study safety assessments (Visit 7).

The schedule of events for Part II is shown in Table 8.1-1 and detailed for visit 2-7 in Table 8.1-2.

Study assessments are described in Section 11.

Table 8.1-1 Schedule of events

Visit	Refer to CSP section	Screening	Part I						Part II	
		Visit 1 Day -28 to -1	Formulation A		Wash-out >4 days	Formulation B		Wash-out and PK calc >14 days	Formulation A or B fed	
			Visit 2 	Visit 3 		Visit 4 	Visit 5 		Visit 6 	Visit 7 
			In-clinic			In-clinic			In-clinic	
Assessment		Day -1 to 2	Day 3	Day -1 to 2	Day 3	Day -1 to 2	Day 3			
Informed Consent	14.3	X								
Inclusion/exclusion criteria	9.4, 9.5	X	X 							
Demographics	11.2.3	X								
Medical/surgical history	11.2.5	X								
HIV, hepatitis B and C	11.2.7	X								
Alcohol breath test	11.2.10	X	X		X			X		
Weight/height (BMI)	11.2.4	X							X 	
Pregnancy Test 	11.2.8	X	X		X			X	X	
Urine Drug Screen 	11.2.9	X 	X	X	X	X		X	X	
Physical Examination	11.4.2	X	X 		X 			X 	X	
Laboratory Safety	11.4.6	X	X	X	X	X		X	X	
Vital Signs	11.4.3	X	X	X	X	X		X	X	
Body temperature	11.4.4		X	X	X	X		X	X	
12-lead ECG	11.4.5	X	X	X	X	X		X	X	
Baseline symptoms	11.2.11	X	X							
IMP administration	10.5		X		X			X		
PK blood sampling 	11.3.1		X	X	X	X		X	X	
Breakfast (standardised)	10.5							X		
Other meals (standardised) 			X		X			X		
Prior/concomitant med.	11.2.6		----- X -----							
AEs 	11.4.1		----- X -----							

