#### 11.4.6 *Laboratory safety assessments*

Blood samples for analysis of clinical chemistry and haematology parameters will be collected through venepuncture or an indwelling venous catheter and sent to the certified clinical chemistry laboratory at Uppsala University Hospital and analysed by routine analytical methods.

Urine analysis will be performed at the research clinic using dip sticks. The assessments will be performed at visits specified in Table 8.1-1.

Urine pregnancy tests will be performed at visits specified in Table 8.1-1.

The safety laboratory parameters are defined in Table 11.4-1 and will be assessed at timepoints detailed in Table 8.1-1.

Safety laboratory parameters will be judged as normal, abnormal NCS or abnormal CS.

Abnormal values assessed by the Investigator as CS will be reported as AEs. If an abnormal value is associated with corresponding clinical signs or symptoms, the sign/symptom should be reported as the AE.

Table 11.4-1 Safety laboratory parameters

Category	Parameter
Clinical chemistry	Alanine aminotransferase (ALT)
	Albumin
	Alkaline phosphatase (ALP)
	Aspartate aminotransferase (AST)
	Bilirubin (total and conjugated)
	C-reactive protein (CRP)
	Calcium
	Creatinine
	Cystatin C
	Glucose
	Potassium
	Sodium
	Urea
Haematology	Haematocrit
	Haemoglobin (Hb)
	Platelet count
	Red blood cell (RBC) count
	White blood cell (WBC) count with differential count
Urinalysis (dip stick)	Bilirubin
	Erythrocytes
	Glucose
	Ketones
	Leucocytes
	Nitrite
	pH
	Protein
	Specific gravity
Urobilinogen	
FSH-test 	FSH
Pregnancy test 	Serum pregnancy test at screening
	Urine pregnancy test

 At screening only

 At screening, post-menopausal females only.

 Females only.

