Assessment	Assessment timepoint	Result	Formulation A/B		
			Formulation A	Formulation B	Formulation A/B
[Parameter 1]	[Assessment timepoint 1]	[RESULT 1]	x(x.x%)/X	x(x.x%)/X	x(x.x%)/X
		[RESULT 2]	x(x.x%)/X	x(x.x%)/X	x(x.x%)/X
	[Assessment timepoint 2]	[RESULT 1]	x(x.x%)/X	x(x.x%)/X	x(x.x%)/X
		[RESULT 2]	x(x.x%)/X	x(x.x%)/X	x(x.x%)/X

Data based on [ANALYSIS SET].
 [STUDYID] [DOMAIN]: [PARAMETER CATEGORY], SAS program: descriptive_stat_tables.sas. Run by: [USERNAME], [USER EMAIL] [TIMESTAMP]

Table 14.3.x.x. ECG – shift table (analysis set)

Assessment	Assessment timepoint	Result	NORMAL	ABNORMAL CS	ABNORMAL NCS	MISSING	TOTAL
			n (%)	n (%)	n (%)	n (%)	n (%)
[Parameter 1]	[Assessment timepoint 1]	NORMAL	X (X%)	X (X%)	X (X%)	X (X%)	X (X%)
		ABNORMAL CS	X (X%)	X (X%)	X (X%)	X (X%)	X (X%)
		ABNORMAL NCS	X (X%)	X (X%)	X (X%)	X (X%)	X (X%)
		MISSING	X (X%)	X (X%)	X (X%)	X (X%)	X (X%)
		TOTAL	X (X%)	X (X%)	X (X%)	X (X%)	X (X%)

Data based on [ANALYSIS SET].
 [STUDYID] [DOMAIN]: [PARAMETER CATEGORY], SAS program: descriptive_stat_tables.sas. Run by: [USERNAME], [USER EMAIL] [TIMESTAMP]

Table 14.3.x.x. Safety laboratory results (analysis set)

[Parameter 1] (unit)	Result Category	Assessment timepoint	Formulation A/B		
			Formulation A	Formulation B	Formulation A/B fed
[Assessment timepoint 1]	Measured value	n	x	x	x
		Mean (SD)	x.xxx (x.xxx)	x.xxx (x.xxx)	x.xxx (x.xxx)
		Median (Min, Max)	x.xxx (x.xx, x.xx)	x.xxx (x.xx, x.xx)	x.xxx (x.xx, x.xx)
[Assessment timepoint 2]	Measured value	n	x	x	x
		Mean (SD)	x.xxx (x.xxx)	x.xxx (x.xxx)	x.xxx (x.xxx)
		Median (Min, Max)	x.xxx (x.xxx, x.xxx)	x.xxx (x.xx, x.xx)	x.xxx (x.xx, x.xx)
Absolute change from baseline	[Assessment timepoint 2]	n	x	x	x
		Mean (SD)	x.xxx (x.xxx)	x.xxx (x.xxx)	x.xxx (x.xxx)
		Median (Min, Max)	x.xxx (x.xxx, x.xxx)	x.xxx (x.xx, x.xx)	x.xxx (x.xx, x.xx)
Relative change from baseline (%)	[Assessment timepoint 2]	n	x	x	x
		Mean (SD)	x.x (x.x)	x.xxx (x.xxx)	x.xxx (x.xxx)
		Median (Min, Max)	x.x (x, x)	x.xxx (x.xx, x.xx)	x.xxx (x.xx, x.xx)

Data based on [ANALYSIS SET].
 [STUDYID] [DOMAIN]: [PARAMETER CATEGORY], SAS program: descriptive_stat_tables.sas. Run by: [USERNAME], [USER EMAIL] [TIMESTAMP]

Clinical chemistry, haematology, coagulation, and urinalysis

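### The mandatory stop for raised ALT with INR above 1.5 has no INR test behind it, and the fourth bullet of Protocol 9.8.3 lets the same subject continue

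*Protocol*

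**What the plan says.** Protocol 9.8.3 opens with a mandatory rule: "Study treatment will be stopped if any of the following liver chemistry stopping criteria" is met. Four triggers follow:

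- ALT 3xULN with bilirubin at least 2xULN (more than 35% direct)
- "ALT 3xULN and INR > 1.5"
- ALT 5xULN
- ALT 3xULN with symptoms suggesting hepatitis or hypersensitivity

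The last bullet of the list is a continuation rule. Subjects with ALT 3xULN but below 5xULN, bilirubin below 2xULN and neither hepatitis symptoms nor rash "will be allowed to continue study treatment as long as they are monitored weekly for four weeks". INR does not appear in it.

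For the tests themselves, Section 11.4.6 says: "Blood samples for analysis of clinical chemistry and haematology parameters will be collected through venepuncture or an indwelling venous catheter". It refers to Table 11.4-1 for the parameters. That table covers chemistry, haematology, dipstick urinalysis, FSH and pregnancy tests. It has no INR or coagulation row. The only extra tests that 9.8.3 mentions are bilirubin fractionation and dipstick bilirubin.

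Two other places mention coagulation in general terms. The Protocol synopsis lists "urinalysis and blood sampling for haematology, clinical chemistry and coagulation parameters", and the SAP layout for safety laboratory results carries the line "Clinical chemistry, haematology, coagulation, and urinalysis". Neither names INR or a time point.

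**The concern.** There are two linked defects. The first is inside 9.8.3: one bullet stops a subject whom another bullet allows to continue. The second is that the result needed to apply the stop is not among the listed tests. Without an INR value the stop cannot fire, so the continuation rule decides by default.

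In practice, an asymptomatic subject with ALT between 3 and 5xULN, bilirubin below 2xULN and an unmeasured INR above 1.5 could receive the next dose. That dose may come as soon as 4 days after Formulation A or, going by the Table 8.1-1 column headed "Wash-out and PK calc >14 days", a little over two weeks after Formulation B. Only an unscheduled INR or a discretionary withdrawal would prevent it.

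The liver is the organ of interest here. Section 6.1.5 identifies hepatobiliary toxicity in dogs as the finding that caps human exposure, and Section 6.3 promises: "The liver biomarkers will be closely monitored during the present study".

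**Working it through.** The plan gives no figure to reproduce. The check is a count of laboratory collections and a comparison of the two rules.

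**Collections that could inform a stop.** Table 8.1-1 marks safety laboratory tests at all seven visits. Table 8.1-2 places them on Day -1 (Visits 2, 4, 6) and at 48 h (Visits 3, 5, 7). There are three doses, at Visits 2, 4 and 6.

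| Collection | Doses already given | Doses still to come | INR listed |
|---|---|---|---|
| Visit 1, screening | 0 | 3 | no |
| Visit 2, Day -1 | 0 | 3 | no |
| Visit 3, 48 h | 1 | 2 | no |
| Visit 4, Day -1 | 1 | 2 | no |
| Visit 5, 48 h | 2 | 1 | no |
| Visit 6, Day -1 | 2 | 1 | no |
| Visit 7, 48 h | 3 | 0 | no |

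Visits 1 and 2 precede any dose and Visit 7 follows the last, so 7 − 3 = 4 collections can lead to a stop before a further dose. INR is listed at 0 of these 4.

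**Stop rule against continuation rule.** Read 3xULN and 5xULN as at or above those values.

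- Stop if (ALT ≥ 3 and bilirubin ≥ 2) or (ALT ≥ 3 and INR > 1.5) or ALT ≥ 5 or (ALT ≥ 3 and symptoms).
- Continue if 3 ≤ ALT < 5 and bilirubin < 2 and no symptoms.

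Apply both to every combination of ALT (2, 3, 4, 4.9, 5, 6 xULN), bilirubin (1, 1.9, 2, 3 xULN), INR (1.0, 1.5, 1.6, 2.0) and symptoms (no, yes): 6 × 4 × 4 × 2 = 192 combinations.

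- The continuation rule covers ALT 3, 4 or 4.9, bilirubin 1 or 1.9, any INR, no symptoms: 3 × 2 × 4 × 1 = 24.
- Of these, the stop rule also applies when INR is 1.6 or 2.0: 3 × 2 × 2 × 1 = 12.
- All 12 conflicts have INR above 1.5. If continuation also required INR ≤ 1.5, the count would fall from 12 to 0.

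The direct-bilirubin fraction is left out. It cannot matter here, because continuation already requires bilirubin below 2xULN. Symptoms are one yes/no flag, so the grid does not test differences in how the two bullets list symptoms.

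**Time before the next dose.** With the minimum wash-out, the interval from Visit 3 to Formulation B is 4 × 24 h − 48 h = 48 h. A first weekly check, 7 days after a raised ALT at Visit 3, would come after that dose. Before the fed dose, a gap of just over 14 days counted from dosing leaves about 14 − 2 = 12 days after Visit 5. That is room for one weekly check; a second needs a gap of at least 2 + 14 = 16 days.

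**The case against.** The best reply is that 9.8.3 is not really contradictory. The opening sentence is mandatory, the last bullet is permissive, and a sensible reader applies the permission only to subjects who have met no stop. That is a fair reading when INR is known. The text does not state it, though, and it gives no help when INR is not measured.

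Second, coagulation does appear in the synopsis and the SAP, and Table 11.4-1 may have lost a row: one of its footnotes, limiting something to screening, has no visible marker. A lost row cannot be excluded. If it carried that footnote, INR would be measured only before dosing. The running text of 11.4.6, which is not part of the table, also leaves coagulation out. At best the documents disagree about whether it is tested.

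Third, there are other safeguards:

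- Continuation requires weekly monitoring. Its content is unspecified, and it comes too late for the shortest interval between Formulations A and B.
- Bleeding and coagulation disorders are excluded and medication is tightly restricted, so non-hepatic causes of a raised INR are unlikely.
- ALT, AST, ALP, albumin and bilirubin are in the panel at each safety draw.
- The investigator may withdraw anyone at discretion (9.8.1).

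These lower the risk, but they do not make the INR criterion usable.

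Finally, the profile is improbable. Serious dog effects occurred with repeated dosing at 80/40 mg/kg, and single doses up to 300 mg gave no noteworthy findings in 36 exposed subjects. That stands, and it limits the weight of the point.

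**Conclusion.** The concern holds. One of four liver stopping triggers cannot be applied from the tests the Protocol lists, at any of the four collections where it could prevent a further dose. For the affected profile (asymptomatic, ALT 3 to below 5xULN, bilirubin below 2xULN, INR above 1.5) the continuation rule gives the opposite instruction. The other three triggers can be assessed from listed tests and adverse event collection.

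The contradiction within 9.8.3 rests on the section's text alone. The statement that INR is not measured on study rests on Table 11.4-1 being complete as it appears, supported by the wording of 11.4.6.

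This should be fixed because it concerns a prespecified safety stop. It is not critical: the event is unlikely in 14 healthy subjects given 120 mg doses, and the PK conclusions are unaffected.

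**What to change.** 1. Add INR (PT) to Section 11.4.6 and Table 11.4-1 at the existing safety-laboratory draws. Alternatively, require a reflex INR whenever ALT is at least 3xULN. In either case, review the result before any further dose.
2. Add to the continuation bullet of 9.8.3 that INR must not exceed 1.5, and state that it applies only to subjects who meet no stopping criterion.
3. Align the coagulation wording in the synopsis and the SAP laboratory layout with the panel chosen.

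The cost is amendment wording plus either one extra analyte on draws already taken or a rarely needed reflex test. After Visit 3 the shortest wash-out still leaves 48 h for the reflex result. After a Day -1 draw only the night before dosing remains, so the amendment should say that dosing waits for the INR.

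The SAP describes the 14 subjects as already dosed. If all dosing is complete, the useful step is to check Visits 3 to 6 for any ALT at or above 3xULN and report whether an INR was obtained before the next dose.

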#### **Duration of treatment**

Subjects will receive in total 3 single doses of GS-248, with a wash-out period of at least 4 days in between each IMP administration.

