#### 8.1.1 Part I: Two formulations of GS-248 in fasting conditions

In Part I of the study, a single oral dose of GS-248 in two different solid formulations will be administered to 14 healthy subjects. All subjects will first receive Formulation A (a lipid-based formulation in a capsule) and then Formulation B (a dry powder in a capsule, see Section 10.1). A wash-out period of at least 4 days will be applied between the IMP administrations. Both doses contain 120 mg GS-248. The rationale for the dose is detailed in Section 8.3.

For Part I, subjects will come to the clinic for 4 visits. At Visit 2, subjects will be admitted to the clinic on the afternoon/evening of Day -1 and will remain at the clinic until Day 2 (24 h post dose) for single dose administration of Formulation A and PK and safety assessments. The subjects must fast for at least 10 hours before the anticipated dosing time on Day 1. Water, but no other drinks, is allowed as desired except for 1 h before and 1 h after dosing. The subjects will be carefully monitored by clinical staff during and after dosing. Vital signs and ECG will be checked at regular intervals as detailed in Table 8.1-2. The subjects will return to the clinic on Day 3 (Visit 3) at 48 h post dose for PK blood sampling and safety assessments, as outlined in Table 8.1-1. Safety assessments include AE reporting, physical

examination, ECG, vital signs, body temperature, and blood sampling for analysis of safety laboratory parameters.

Visit 4 will be similar to Visit 2, at which subjects will stay overnight at the clinic from Day -1 to Day 2 for single dose administration of Formulation B and PK blood sampling and safety assessments. Visit 5 will be similar to Visit 3, at which subjects return to the clinic on Day 3 for PK blood sampling and safety assessments.

The schedule of events for Part I is shown in Table 8.1-1 and detailed for visit 2-7 in Table 8.1-2.

Study assessments are described in Section 11.

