#### *11.4.1.15 Treatment and follow-up of adverse events*

Subjects with AEs that occur during the study must be treated according to daily clinical practice at the discretion of the Investigator.

AEs must be followed up until resolution or to the end-of-study visit, whichever comes first. At the end-of-study visit, information on new AEs, if any, and stop dates for previously reported AEs must be recorded (if known). AEs assessed as stable by the Investigator at the end-of-study visit will not have to be followed up until resolution.

It is the responsibility of the Investigator to follow up on all SAEs until the subject has recovered, stabilised, or recovered with sequelae, and to report to the Sponsor all relevant new information using the same procedures and timelines as those for the initial report. Relevant information includes discharge summaries, autopsy reports, and medical consultation.

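### The four weeks of weekly liver checks that section 9.8.3 makes a condition of continued dosing cannot be met within the scheduled visits and the stated end of follow-up

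*Protocol*

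**What the plan says.** **The condition.** The last bullet of protocol section 9.8.3 covers a subject with ALT from 3 to below 5 times ULN, bilirubin below 2 times ULN and no hepatitis symptoms or rash. Such subjects "will be allowed to continue study treatment as long as they are monitored weekly for four weeks". The bullet does not say at which visits the checks take place, or whether any check must come before the next dose.

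**The doses.** Each subject receives three single doses. Section 8.1.1 says: "A wash-out period of at least 4 days will be applied between the IMP administrations". The synopsis (Duration of treatment) applies that minimum to every interval, "with a wash-out period of at least 4 days in between each IMP administration", and section 8.2 agrees. Table 8.1-1 differs: it shows more than 4 days before Formulation B and, before the fed dose, "Wash-out and PK calc >14 days".

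**The liver samples.** Section 11.4.6 says that the safety laboratory parameters "will be assessed at timepoints detailed in Table 8.1-1". Tables 8.1-1 and 8.1-2 place them at screening, on Day -1 of Visits 2, 4 and 6, and at 48 h after each dose (Visits 3, 5 and 7). Neither table has a weekly liver row.

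**The end of contact.** Visit 7, 48 h after the third dose, is the end-of-study visit. Section 11.4.1.15 says: "AEs must be followed up until resolution or to the end-of-study visit, whichever comes first". It adds that events judged stable at that visit need not be followed to resolution. Only serious events are explicitly followed further.

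**The concern.** The continuation bullet reads like a rule for continuous dosing, where weekly samples over four weeks run alongside treatment. This study gives three isolated doses over a short period and then ends contact. If staff follow the visit tables and section 11.4.1.15 as written, a subject with raised ALT can be given another dose on a condition that lapses before it is fulfilled.

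The liver is the organ that matters most here. Section 6.1.5 names liver and biliary toxicity in dogs as the finding that limits human exposure. Section 6.3 answers that risk with a promise of close monitoring of liver biomarkers, and section 9.8.3 contains the operative rules for acting on a raised value. A gap between that section and the schedule is therefore a gap in a safety rule, even if it is seldom triggered.

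**Working it through.** **Inputs** (days counted from the first dose as day 0)
- w1 = days from dose 1 to dose 2: at least 4 (section 8.1.1).
- w2 = days from dose 2 to dose 3: more than 14 (Table 8.1-1), or at least 4 (synopsis, section 8.2).
- Safety samples: 1 day before and 2 days after each dose.
- Last contact, Visit 7: w1 + w2 + 2.
- Monitoring required: checks at +7, +14, +21 and +28 days from the flag, so 28 days of contact.

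**The plan's own figure.** Section 8.1 plans about 8 weeks per subject, including up to 4 weeks of screening. The minimum is 28 + 4 + 14 + 2 = 48 days, or 6.9 weeks. Intervals of 8 and 18 days give 28 + 8 + 18 + 2 = 56 days, exactly 8 weeks. The stated duration is therefore consistent with the schedule, and both cases are used below.

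**Scheduled contact left after a flag** = (w1 + w2 + 2) minus the day of the flagged sample.

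| Flagged sample | Formula | 4/14 days | 8/18 days | 4/4 days |
|---|---|---|---|---|
| Visit 3 (48 h) | w1 + w2 | 18 | 26 | 8 |
| Visit 4 Day -1 | w2 + 3 | 17 | 21 | 7 |
| Visit 5 (48 h) | w2 | 14 | 18 | 4 |
| Visit 6 Day -1 | 1 + 2 | 3 | 3 | 3 |
| Visit 7 (48 h) | 0 | 0 | 0 | 0 |

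Every entry is below 28. The Visit 6 Day -1 entry does not depend on the wash-outs: the dose is scheduled 1 day after the flag, and contact ends 2 days after the dose.

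**How many weekly checks do the scheduled samples deliver?** After a Visit 3 flag the later samples fall at +(w1 - 3), +w1, +(w1 + w2 - 3) and +(w1 + w2), which is two pairs with 3 days inside each pair. Allow each check to be 1 day early or late. The windows are then days 6 to 8, 13 to 15, 20 to 22 and 27 to 29, with 5 days between one window and the next. A pair 3 days apart can meet at most one check, so scheduled samples meet at most two of the four whatever the wash-outs. On the 4/14 schedule the samples fall at +1, +4, +15 and +18, and only the second check is met.

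**Flag to next dose.** From Visit 3 to the earliest Formulation B dose is 4 - 2 = 2 days. The Visit 4 Day -1 sample falls between them, 1 day after the flag, and the first weekly check is due 5 days after that dose. If the wash-out is counted from Visit 3 instead, the gap is 4 days, still before the first check. From Visit 5 to the fed dose is 14 - 2 = 12 days under Table 8.1-1, but 4 - 2 = 2 days under the synopsis and section 8.2.

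**The case against.** The strongest reply is that section 9.8.3 is itself the instruction to monitor. Procedures triggered by an event need not appear in a routine schedule: the repeat ECGs in section 9.8.2 are not in Table 8.1-2 either. Nothing forbids unscheduled visits, and the wash-outs are minima. If the two intervals total 28 days, a Visit 3 flag has its full window, with Visit 7 on day 30 and participation of 28 + 30 = 58 days, or 8.3 weeks. Section 9.8.1 also lets the investigator withdraw a subject at any time.

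Much of this stands, and it rules out four stronger readings that a reader might infer.
- *The condition can never be met.* The documents do not exclude extra visits. They only fail to provide for them.
- *A dose 2 days after a flag breaches the rule.* The rule lets dosing go on while monitoring runs and does not say that a check must come first. This is an ambiguity, not a breach.
- *Re-dosing happens with no repeat value.* The Day -1 samples at Visits 4 and 6 give one, although the documents do not state when the result is available.
- *A flag at Visit 7 violates section 9.8.3.* No dose remains, so the condition for continuing does not apply. Only a follow-up question is left.

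Section 11.4.1.15 is also not a clean override. It governs adverse events, and under section 11.4.6 a laboratory value becomes one only if judged clinically significant. Its sentence on stable events suggests that unstable ones might be followed longer, which sits awkwardly with the rule that follow-up stops at the end-of-study visit.

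The reply does not remove the mismatch. The repeat ECGs are taken within a brief period, whereas the liver monitoring outlasts the study's scheduled contact. Longer wash-outs do not help a Visit 6 Day -1 flag, and no wash-out makes the scheduled samples weekly.

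**Conclusion.** The point holds in this form: the monitoring on which continued dosing depends cannot be met within the scheduled visits and the stated end of follow-up. Against 28 days required, the minimum schedule leaves 18 days after a Visit 3 flag, 14 after a Visit 5 flag and 3 after a Visit 6 Day -1 flag. Participation of 8 weeks with full-length screening raises the longest window to about 26. The clearest case is the Visit 6 Day -1 flag, where the bullet allows a dose the next day and scheduled contact ends 3 days after the flag. Separately, section 9.8.3 leaves open whether Formulation B may be given before any weekly check.

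Assumptions: weekly means every 7 days, the flag is dated at sampling (any laboratory delay shortens the time to the next dose), wash-outs run from dose to dose, and a check may be 1 day early or late. The documents do not say how many subjects would meet the bullet. I assume few.

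**What to change.** Reconcile section 9.8.3 with the visit schedule in section 8.1 (Tables 8.1-1 and 8.1-2) and with the follow-up rule in section 11.4.1.15, so that the condition for continued dosing and the end of follow-up agree. In the same edit, settle the interval before the fed dose, which is at least 4 days in the synopsis and section 8.2 but more than 14 days in Table 8.1-1. The text should state how the next single dose relates to the required checks, and which passage governs after Visit 7. Both are the sponsor's decisions, and no clinical rule is proposed here.

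The cost is protocol wording. Depending on the decision, a flagged subject might have unscheduled samples or a delayed period or exit. Blood volume leaves room for samples: section 12.2 estimates about 300 mL against a ceiling of 450 mL, a margin of 150 mL.
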